Photo-plethysmography (PPG) is a promising technology used in smartphones and smartwatches for heartrate and rhythm assessment. (6) To retrieve PPG measurements a photo-emitter of infrared light is coupled to a photo-receiver. The amount of infrared light absorbed or reflected by blood represents the systolic and diastolic phase. This technology has low costs and does not require additional hardware. Although easy to use and widely available, PPG measurements require good signal quality which may be affected by poorly perfused tissue or tremors. Especially in AF detection proper signal-noise assessment is important because of the irregular depolarization of the ventricles. To overcome these previous issues, we developed an automated PPG based diagnostic algorithm for the smartphone to detect AF. The test characteristics of this technique are robust and described elsewhere. (7)

Principal investigators and steering committee:

Dr. [name], cardiologist, Rijnstate hospital Arnhem

Dr. [name], geriatrician, North West Clinics, Alkmaar

Dr. [name], cardiologist Rijnstate hospital, Arnhem

Dr. [name], cardiologist, OLVG, Amsterdam

Dr [name], cardiologist, North West Clinics, Alkmaar

Participating centers:

Dijklander Hospital, Hoorn. Drs. [name], geriatrician.

Meander Medical Centre, Amersfoort. Drs. [name], geriatrician.

North West Clinics, Alkmaar. [name][name], geriatrician.

Rijnstate Hospital, Arnhem. [name], geriatrician.

Onze Lieve Vrouwe Gasthuis, Amsterdam. [name], cardiologist.

Aims of the project:

- a. To determine the rate of newly detected AF with repeated screening using a PPG based smartphone AF detection algorithm during follow-up visits at a geriatric outpatient center.
- b. To determine the rate of (paroxysmal) AF during follow-up visits.
- c. To evaluate the predictive value of a single measurement of NTproBNP at the baseline evaluation for the development of new AF.
- d. To evaluate the predictive value of the ABC Bleeding Risk Score, compared to the ATRIA Bleeding Risk Score, ORBIT Bleeding Risk Score, and HASBLED score.
- e. To evaluate adverse events such as major bleeding, stroke, death and cognitive disorders (Mild Cognitive Impairment or dementia), on the long term, namely: 3 years.

Hypothesis:

- a. We expect to find a rate of known AF of approximately 20%, and to find newly detected AF in 4 to 5% of the screened population.

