- b. We expect to find a rate of paroxysmal AF of 45 to 60%.
- c. We expect that the baseline level of NTproBNP or BNP will be predictive of the development of new AF, especially when combined with the findings of the comprehensive geriatric assessment (CGA) and CHA₂DS₂Vasc score.
- d. We expect a rate of major bleeding of 3-5% per year.
- e. We expect that the ABC bleeding score, using age, GDF-15 and high sensitive Troponin T, will be predictive of major bleeding in the geriatric population.

Design:

- a. Prospective multicentre cohort study
- b. We aim to include 1250 geriatric ambulatory patients
- c. Inclusion period will last for 6 months, with a consecutive follow up period of 6 months, at 3 years patient files will be accessed for adverse events
- d. Scheduled commencement of the study is October 2020
- e. Blinding: none
- f. Randomization: none

Ethical board:

- a. The Commission Human Bound Research region Arnhem-Nijmegen, The Netherlands, has exempted the protocol as a 'niet WMO-plichtig onderzoek'.
- b. The record number of this decision is: 2019-5889.

Methods:

- a. The PPG measurements will be performed with a specially designed app, this research app will be developed by Happitech. Every participating center will receive a smartphone in order to install the application.

- b. All newly referred patients of 65 years and older that visit geriatric outpatient services are eligible (including Fall clinic, Memory clinic, Pre-operative geriatric assessment clinic, or any other geriatric outpatient clinics that are led by a geriatrician).
- c. Patients will be sent printed informative material about the project together with their appointment details. This material includes the informed consent form. They are asked to read the material, and fill out the informed consent form at home. At arrival to the outpatient clinic remaining questions will be answered, and the informed consent form collected, scanned, and added to their electronic medical file.
- d. Inclusion criteria:
 - a. The patient is able and willing to give written informed consent or allows a representative to do so in their name.
 - b. The paper copy will remain at the outpatient clinic to serve as a backup.
- e. Exclusion criteria:
 - a. The patient has a pacemaker or implantable cardioverter defibrillator.
 - b. The patient is known with a severe dementia, MoCA \leq 15 points.

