 - c. The patient has a severe tremor, from whatever cause, and thus is unable to use the PPG based smartphone AF detection algorithm.
- f. Exclusion from analysis:
 - a. Less than three measurements with the PPG based smartphone AF detection are performed.
- g. Procedure (See also Figure 1, on page 5):
 - a. All participating patients will be allocated a study number. The allocation of study numbers will be coordinated by the research nurse, in collaboration with the local investigator and secretary. To ensure patient privacy, it is not allowed to use the hospital's patient number as the study number. Predefined study numbers will be provided to each centre.
 - b. The study number will be communicated with the physician by the secretary, and added to the electronic hospital files.
 - c. A CGA will be performed at baseline.
 - d. A 12 lead ECG will be performed at study entry to assess the baseline heart rhythm.
 - e. At every visit to the outpatient service one measurement with the PPG based smartphone AF detection algorithm will be performed.
 - f. The application will be made available for patients to install on their own smartphone, or their caretaker's.
 - g. Before each measurement the physician/patient/caretaker enters the patient's study number into the PPG app, which allows the investigators to register which measurement belongs to which participant, without accessing their medical files.
 - h. Coded, raw data will be analysed by the app, and results automatically sent by email to the principle investigator ([name]).
 - i. The smartphone shows the measurement in real time. In case of artefacts due to movement or otherwise, the PPG based smartphone AF detection algorithm will reveal this and a repeat measurement will be performed.
 - j. In case the PPG based smartphone AF detection algorithm detects AF, a 12 lead ECG is performed to confirm and document the diagnosis of AF and appropriate treatment will be initiated by the treating physician.

- k. If AF is detected at home, patients will be invited for the 12 lead ECG in the outpatient clinic.
 - l. Only patients who are known with AF and have an ECG or Holter registration showing AF in their medical record will be classified as patients with 'known AF'.

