- m. Patients will be classified as 'newly detected AF' if AF is detected by the PPG device and consecutively confirmed on a 12 lead ECG. These ECGs will be periodically collected by the research nurse, in order to be reviewed to confirm the diagnosis for research purposes, by an independent cardiologist ([name] or [name]).
- n. All positive measurements with the PPG based smartphone AF detection algorithm, will be assessed by an independent cardiologist ([name] or [name]).
- o. Patients known with AF will also be screened with the device in the same fashion, making it possible to estimate the proportion of paroxysmal AF, but a confirmatory ECG will not be necessary as AF is already documented in those patients.
- p. In patients with newly detected AF, the algorithm will still be used in follow up visits, in order to determine the rate of paroxysmal AF.
- q. At study entry the baseline characteristics will be collected, including:
 - i. Medical history and medication use (as part of the CGA).
 - ii. MoCA.
 - iii. Functional measures such as pattern of gait and muscle weakness (as part of the CGA) and basic measurements such as weight and blood pressure (as part of the CGA)
 - iv. Standard blood samples including kidney function, blood count, electrolytes and INR if applicable. Blood will be taken during the routine blood sampling, to assess the HS Troponine T, NTproBNP and GDF-15 at an external location (Dijklander Hospital). A separate protocol can be found on page 6 of this protocol.
- r. Information about the study will be available in print at every participating centre. This information folder is added as an attachment.
- s. Of all patients at least 3 measurements with the PPG based smartphone AF detection algorithm will be collected, including the measurement at study entry, during a 6 months follow-up period. After 3 years adverse events will be assessed.
- t. A designated research nurse will have access to the code list (patient identifier and study code) at each participating centre collect participating centres, collect data on the baseline characteristics, and the measurements with the PPG based smartphone AF detection algorithm.

[figure not shown]

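### The exclusion of patients with fewer than three PPG measurements has no stated scope; as written it also restricts the baseline, bleeding-score and 3-year outcome analyses to patients who survived to and had a third reading

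*Combined protocol and SAP*

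**What the plan says.** - **The rule.** Methods f, the only analysis-set rule in the visible text (Figure 1 was not available to check), removes a patient when "Less than three measurements with the PPG based smartphone AF detection are performed". It names no aim, outcome or SAP section. The SAP defines no analysis population and neither repeats nor limits the rule.
- **Planned readings.** Methods g (Procedure), item s, plans at least three readings per patient within 6 months, counting the one at entry. Readings need not be in clinic. Item f says "The application will be made available for patients to install on their own smartphone".
- **New AF.** Under Procedure item m a patient counts as a new case "if AF is detected by the PPG device and consecutively confirmed on a 12 lead ECG", with no minimum number of readings. Item p adds: "In patients with newly detected AF, the algorithm will still be used in follow up visits".
- **Long-term outcomes.** Methods m has every patient's file checked at 3 years for major bleeding, stroke, death and cognitive disorders. SAP 2.2 compares the bleeding scores, and SAP 4, item 3, models death and major bleeding.
- **Main aim.** Aim a is "To determine the rate of newly detected AF with repeated screening", and hypothesis a expects "newly detected AF in 4 to 5% of the screened population".

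**The concern.** Having a third reading is a post-baseline event. It requires that the patient is still alive and either returns to the clinic or uses the app at home. That condition makes sense for a question about repeated rhythm measurement. It does not for bleeding scores calculated from baseline data, a baseline comparison of patients in sinus rhythm with patients with known AF, or outcomes read from the files at 3 years.

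If the rule governs those analyses, three things follow:
- A patient who dies before the third reading is removed, although the death is known and is an outcome that aim e counts. Bleeds and strokes in patients who never reach a third reading go too.
- Patients who stay in cannot have died before their third reading. If time is counted from study entry, that interval is guaranteed survival time.
- Because the scope is not written down, two analysts could use different populations for the same aim, and the choice could be made after the data are seen.

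There is a smaller issue for aim a. A new case confirmed at reading 1 or 2 leaves both numerator and denominator if no third reading follows.

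**Working it through.** The documents give no mortality, no timing of the third reading and no expected share of patients with fewer than three readings, so there is no plan figure to reproduce. Those inputs are assumptions below. From the documents: 1250 patients (Design b), 4–5% new AF (hypothesis a), major bleeding 3–5% per year (hypothesis d), the 6-month reading window (Procedure s) and the 3-year file check (Methods m).

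**1. Which analyses need three readings?**
- SAP 2.1 uses rhythm at baseline, from the entry ECG and the medical record: no.
- SAP 2.2 uses baseline scores and later bleeding: no.
- SAP 4, item 3, and aim e use outcomes from the file check: no.
- Aims a to c, SAP 3 and SAP 4, items 1 and 2, rest on PPG-detected rhythm: repeated readings matter.

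**2. Share of 3-year deaths that the rule removes.** With constant mortality m per year and the third reading at time t (years), the share is (1 − exp(−m·t)) / (1 − exp(−3m)).

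| Third reading at | m = 0.05 | m = 0.15 |
|---|---|---|
| 7 days | 0.7% | 0.8% |
| 1 month | 3.0% | 3.4% |
| 3 months | 8.9% | 10.2% |
| 6 months (all patients; upper bound) | 17.7% | 19.9% |

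Example, 3 months and m = 0.05: (1 − exp(−0.0125)) / (1 − exp(−0.15)) = 0.0124 / 0.1393 = 8.9%. This is the share of deaths lost, not the bias in reported mortality.

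**3. Net effect on reported 3-year mortality.** Assume that 30% stop for reasons other than death, the others die at 10% per year, and the third reading is at 3 months.
- Analysed set: 1 − exp(−0.10 × 2.75) = 24.0%.
- All patients: 0.3 × (1 − exp(−3h)) + 0.7 × (1 − exp(−0.30)), where h is the yearly mortality of those who stop. This gives 25.9% for h = 0.10, 22.3% for h = 0.05 and 31.7% for h = 0.20.

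The analysed figure can therefore lie on either side of the true one.

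**4. Bleeding events.** With all 1250 patients and competing death ignored, 1250 × (1 − exp(−3r)) gives about 108 patients with a major bleed by 3 years at r = 0.03 and 174 at r = 0.05. If 20% are excluded and have equal risk, 86 to 139 remain. This shows lost information only, not a change in any AUC.

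**5. Aim a.** Let each reading independently detect a share q of patients with AF, so that n readings detect d_n = 1 − (1 − q)^n. Let three readings yield 5.0%, so that AF prevalence is 0.05/d_3. A share f of patients, unrelated to AF, have only one or two readings (half each).
- Three-reading set: exactly 5.0%, by construction.
- One-or-more set: (0.05/d_3) × [(1 − f)·d_3 + (f/2)·d_1 + (f/2)·d_2]. For q = 0.3: 4.6% (f = 0.2) and 4.2% (f = 0.4). For q = 0.5: 4.7% and 4.4%.
- At f = 0.2, detected cases are retained at 0.8 × 0.05 / 0.0462 = 87% (q = 0.3) or 0.8 × 0.05 / 0.0471 = 85% (q = 0.5), and non-cases at about 80%. Unequal retention therefore does not by itself show bias.

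**6. Confirmed cases that could be dropped.** 4–5% of 1250 is 50 to 62.5 cases. If two thirds are found at reading 1 or 2 and 20% of those have no third reading (both assumed), 50 × 2/3 × 0.2 = 6.7 to 62.5 × 2/3 × 0.2 = 8.3, or about 7 to 8 cases. Cases found at reading 3 or later cannot be lost this way.

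**The case against.** **The plan intends complete data.** Procedure s plans three readings for everyone, Procedure p continues them after detection, and Methods m covers every file at 3 years. On that reading nobody is lost, or everyone is meant to be analysed at 3 years. Part of this stands: a reader might infer that the sponsor means to discard early deaths, and the documents do not show that. But the exclusion operates only where the intention of three readings fails, and Methods m describes data collection. No visible text exempts any analysis.

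**Three readings may be complete within days.** Home readings count, so it would be wrong to say that a patient must attend three visits. This stands, and it is why the range begins at 0.7–0.8%.

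**Mortality need not be understated.** A reader might infer that dropping early deaths makes reported mortality too low. Removing those deaths alone does lower it, but the rule also drops living patients who stop, and their risk is unknown. Eligible services range widely ("including Fall clinic, Memory clinic, Pre-operative geriatric assessment clinic"), so their risk could be lower or higher.

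**Discrimination may be unaffected.** The scores would be compared in the same patients whichever set is used. This stands: nothing here shows a change in AUC, sensitivity or specificity.

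**Three readings are right for aim a.** A reader might infer that the rule biases the new-AF rate. The documents do not support that. The aim concerns repeated screening, and when dropout is unrelated to AF the three-reading set returns the intended rate while the wider set reads low. Dropout related to detection could shift the rate either way, but the documents give no evidence of it.

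**Conclusion.** For the 3-year outcomes, the bleeding scores and the baseline comparison, the rule is wrong as written. It makes entry depend on a post-baseline event that these analyses do not need, and the 3-year population is left unclear. That follows from the text. The size does not: between 0.7% and 20% of 3-year deaths would be removed, depending almost wholly on when the third reading falls, under constant mortality of 5–15% per year. The upper end requires every third reading to fall at 6 months. No direction can be given for net mortality.

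For aim a there is no demonstrated error. The choice of set is a trade-off, and a second, clearly labelled estimate is a cheap improvement.

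**What to change.** 1. State in Methods f and in the SAP that the three-measurement minimum applies only to the PPG-based rhythm analyses.
2. For SAP 2.1, SAP 2.2, SAP 4, item 3, and the adverse events of aim e, include all consented patients with the needed baseline data, followed from study entry, whatever their number of PPG readings.
3. For aim a, name the three-reading set in advance as the main estimate. As a sensitivity analysis, report the rate in all patients with at least one readable measurement, cases and non-cases alike. Do not add back early cases alone: with a true 5.0% and 80% of non-cases retained, that would read 0.05 / (0.05 + 0.95 × 0.8) = 6.2%.
4. Report how many patients had 1, 2, and 3 or more readings. Use the same denominator rule in both sets. Whether it includes known AF is a separate choice, since "Patients known with AF will also be screened with the device in the same fashion".

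The cost is wording; no new data are needed. The drawback lies in the aim a sensitivity analysis: some patients in the wider set are thinly screened, which dilutes the rate to about 4.2–4.7% against 5.0% under the values assumed in step 5. It should be presented with that caveat.

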The Dutch multicentre study into opportunistically screening Geriatric patients for Atrial Fibrillation using a PPG smartphone App; the Dutch-GERAf Study

Outline of the healthcare innovation project

Background of the project:

The latest European Cardiology Society's guideline (1. Kirchhof et al.) on the management of atrial fibrillation (AF) recommends opportunistic screening for people 65 years and older, and systematic screening might be considered in high risk population. The geriatric population that visits the outpatient service is such a population. Our previous work (2. Zwart et al., 3. Zwart et al.) showed that geriatric patients have a high rate of AF, and furthermore a very high rate of newly detected AF can be found when repeated screening is applied.

Since AF in elderly people often exists without symptoms, paroxysmal AF can easily remain undetected, and therefore untreated (2. Zwart et al.). Because geriatric patients have a very high risk of risk it is very relevant to identify cases of silent AF. To know the rate of paroxysmal AF helps to estimate the magnitude of the problem, and what the yield of repeated screening for AF might be in this population.

However, repeated screening for AF is not the common geriatric practise at this moment. It is very relevant to determine if comparable results are found when repeated screening is applied in multiple geriatric practises, and with a different method of detection. The primary goal of this innovation project is to assess the rate of newly detected AF when using a smartphone-based PPG detection app, and to determine if repeated screening for AF should become standard geriatric practise. This innovation project seeks to address those questions.

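### Items l and m let a patient with an earlier AF diagnosis but no tracing on file count as newly detected AF, which may inflate the primary rate

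*Combined protocol and SAP*

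**What the plan says.** The project's main aim is stated in the background section: "The primary goal of this innovation project is to assess the rate of newly detected AF when using a smartphone-based PPG detection app". The result is also meant to help decide whether repeated screening should become standard geriatric practice.

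Three rules in the Methods determine who counts as a new case.

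- **Item b (eligibility):** "All newly referred patients of 65 years and older that visit geriatric outpatient services are eligible".
- **Procedure, item l:** "Only patients who are known with AF and have an ECG or Holter registration showing AF in their medical record" are classed as known AF. There are two conditions, a diagnosis and a tracing, and both must hold. No date limit is set on the tracing.
- **Procedure, item m:** "Patients will be classified as 'newly detected AF' if AF is detected by the PPG device and consecutively confirmed on a 12 lead ECG". Earlier history is not mentioned.

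Item d gives every participant a 12-lead ECG at study entry. The available text does not say how AF on that ECG is classified. Item q.i collects medical history and medication use at baseline. The SAP compares sinus rhythm with known AF at baseline (2.1) and sinus rhythm throughout with newly detected AF (3.1). It then models predictors of newly detected AF (section 4). There is no class for an earlier diagnosis without a tracing.

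**The concern.** The two definitions are not complements. A patient whose history records AF but whose record holds no tracing fails item l. Under item o only patients with documented AF are spared the confirmatory ECG, so this patient would have one after a positive PPG (item j). If it shows AF, item m is met. The independent cardiologist review in items m and n establishes that AF is present, not that it is new.

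The rationale for screening is silent AF that would otherwise go undetected and untreated. Finding AF again in someone already diagnosed is not that yield. In the primary numerator the error can only run upward, and a larger sample would not reduce it.

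The secondary analyses are exposed as well. Untraced patients who show AF enter SAP 3.1 and 4 as new cases although their AF is established. Those who never show it during screening could fall into the comparison group with sinus rhythm throughout.

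**Working it through.** The plan gives no calculation of this effect, so there is no figure to reproduce. What follows is a sensitivity calculation.

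**Inputs from the documents**

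- Sample size (Design, item b): "We aim to include 1250 geriatric ambulatory patients".
- Expected rates (Hypothesis a): about 20% with known AF, and 4 to 5% with newly detected AF, the latter as a share of those screened.
- Paroxysmal share (Hypothesis b): "We expect to find a rate of paroxysmal AF of 45 to 60" per cent, so par = 0.45 to 0.60 and the non-paroxysmal share is 0.40 to 0.55.
- At least three PPG readings per patient, including the one at entry (item s).

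**Assumptions not in the documents**

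- u, the share of patients with earlier AF who have no tracing: 5%, 10% or 20%.
- p, the chance that a paroxysmal patient is in AF at any one reading: 0.1 to 0.3, independent between readings.
- The expected known-AF group stands in for all patients with an earlier diagnosis: 1250 × 0.20 = 250.

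**Benchmark.** Expected new cases are 1250 × 0.04 = 50 to 1250 × 0.05 = 62.5. The 95% half-width is 1.96 × √(p̂(1 − p̂)/1250), which is 1.1 points at p̂ = 4% and 1.2 points at p̂ = 5%.

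**Reading A: AF on the entry ECG satisfies item l.** A patient with a history who is in AF at entry then becomes known. Only paroxysmal patients remain who are out of AF at entry and in AF at reading 2 or 3:

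d = par × (1 − p) × [1 − (1 − p)²]

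- Low: 0.45 × 0.9 × 0.19 = 0.077
- High: 0.60 × 0.7 × 0.51 = 0.214

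**Reading B: the tracing must predate entry.** The lowest value counts non-paroxysmal patients alone, d = 0.40. Adding paroxysmal patients caught at any of three readings gives d = 1 − par × (1 − p)³:

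- Low: 1 − 0.60 × 0.729 = 0.563
- High: 1 − 0.45 × 0.343 = 0.846

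The range for B is therefore 0.40 to 0.846.

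**Excess cases** = 250 × u × d; **points** = 100 × excess / 1250.

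| u (assumed) | Untraced patients | Reading A | Reading B |
|---|---|---|---|
| 5% | 12.5 | 1.0 to 2.7 (0.1 to 0.2 points) | 5.0 to 10.6 (0.4 to 0.8 points) |
| 10% | 25 | 1.9 to 5.4 (0.2 to 0.4 points) | 10.0 to 21.1 (0.8 to 1.7 points) |
| 20% | 50 | 3.8 to 10.7 (0.3 to 0.9 points) | 20.0 to 42.3 (1.6 to 3.4 points) |

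At u = 0 the excess is zero. Where paroxysmal patients are counted, the figures lean high, because the confirming ECG must also catch AF, and after a home reading it is taken at a later clinic visit (item k).

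**The case against.** Four objections carry weight.

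1. **A missing tracing does not by itself make a new case.** A reader might infer from item l that every untraced patient becomes newly detected AF. Item m does not support that: PPG and ECG must both show AF. With 45 to 60% paroxysmal AF expected, many such patients may never meet it. This stands, and it is why the calculation carries a detection probability.

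2. **The number of such patients is unknown.** Newly referred to geriatrics does not mean new to the hospital. Item l speaks of the patient's medical record and does not require that the tracing was made in that hospital, so tracings obtained from elsewhere could satisfy it. This also stands. The documents allow inflation but do not show that it occurs.

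3. **The entry ECG may absorb most of the problem.** If AF on that ECG counts as the tracing, reading A applies and the effect is small. The text permits this reading but does not settle it. The same patient could meet both item l and item m, which is a further reason to state the timing.

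4. **Item l is a sensible verification rule.** It keeps unverified labels out of known AF. Excluding patients on an unverified historical diagnosis could push the rate too low. That is a fair trade-off, and reporting the rate both ways answers it.

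Figure 1 is not available here and may carry further detail on classification.

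**Conclusion.** The gap stands as a matter of wording: followed literally, items l and m can place previously diagnosed AF in the numerator of the primary outcome. Any resulting bias in that numerator is upward.

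Its size cannot be stated from the documents. With a 10% untraced share it would be small compared with sampling error under reading A, and about as large as the 1.1 to 1.2 point half-width, or somewhat larger, under reading B. Both rest on the assumed u and p and on 250 as a stand-in for all patients with earlier AF.

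Two stronger conclusions may tempt a reader. The first is that the plan does inflate its primary rate. Only *may inflate* is supported, since the untraced share could be near zero. The second is a larger effect in points, obtained by dividing by the 1000 patients expected to be without known AF. The plan expresses its 4 to 5% as a share of the screened population, and item o screens known-AF patients too, so 1250 is the basis used here.

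The point should be settled in the plan because the rate is meant to inform a decision about routine practice.

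**What to change.** 1. **Item m:** add *and no diagnosis of AF was recorded in the medical history before study entry*.
2. **Item l:** state that the tracing must predate study entry. This removes the overlap with the entry ECG.
3. **New baseline class:** *previously diagnosed AF without available tracing*. Flag it from the medical history and medication use already collected under item q.i, before screening results are known, since the study is unblinded. Item q.i does not name referral letters or medication indication, so the rule should not depend on them unless they are added.
4. **Analysis:** leave this class out of the primary newly detected rate and out of the new-AF analyses in SAP 3.1 and 4. Report the rate with the class counted as new as a sensitivity analysis.

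The cost is a sentence in each of two items, one baseline field and one extra line in the results. No visit or test is added. The downside is a slightly lower newly detected rate, and a few patients with an unverified historical label leave the at-risk group. If few patients fall in the class, the two reported rates will show that it made little difference.

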3.2 Multivariate analysis

Correction/multivariate analysis of significant differences found in the univariate analysis 3.1

4. Multivariate analysis / Regression analysis

1. Factors predicting newly detected AF
2. NT-proBNP and/or GDF-15 predicting newly detected AF
3. Factors predicting death, or major bleeding, or composite outcome (death + major bleeding)

References

3. Zwart LAR, Jansen RWMM, Germans T, Simsek S, Ruiter JH, Hemels MEW. Opportunistic screening for atrial fibrillation with a single lead device in geriatric patients. Journal of Geriatric Cardiology (2020) 17: 149-154.
5. Rockwood K and Mitnitski A. Frailty in relation to the accumulation of deficits. Journal of Gerontology 2007, Vol. 62A, No. 7, 722-727.
7. Riezebos K et al. Article in press in HRS Cardiovascular Digital Health Journal.

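### The NT-proBNP analysis for aim c (SAP 4, item 2) can count AF already confirmed at study entry as AF that the baseline sample predicted

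*Combined protocol and SAP*

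**What the plan says.** **The question.** Aim c is "To evaluate the predictive value of a single measurement of NTproBNP at the baseline evaluation for the development of new AF". Hypothesis c matches it: "We expect that the baseline level of NTproBNP or BNP will be predictive of the development of new AF".

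**The analysis.** SAP 4, item 2 reads "NT-proBNP and/or GDF-15 predicting newly detected AF". It states no at-risk population and no time window.

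**The outcome.** Under Methods item g.m, a patient is newly detected AF "if AF is detected by the PPG device and consecutively confirmed on a 12 lead ECG". At least three PPG readings are required per patient, "including the measurement at study entry, during a 6 months follow-up period" (item g.s).

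**Entry procedures.** "A 12 lead ECG will be performed at study entry to assess the baseline heart rhythm" (item g.d). "At study entry the baseline characteristics will be collected" (item g.q), and the blood for NT-proBNP, GDF-15 and troponin T is on that list.

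**Known AF.** "Only patients who are known with AF and have an ECG or Holter registration showing AF in their medical record will be classified" as such (item g.l).

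**SAP groups.** SAP 2.1 compares patients in sinus rhythm at baseline with patients with known AF. SAP 3.1 compares patients who stay in sinus rhythm throughout with patients with newly detected AF.

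**The concern.** Prediction needs a marker measured before the event, in people who do not yet have the event. A patient with undiagnosed AF who is PPG-positive and ECG-confirmed at entry already has AF at the visit where the blood is listed. For that patient the link between NT-proBNP and AF is diagnostic.

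The written outcome puts this patient in the same group as one whose AF is first found months later. If the plan is followed as written, one regression on the mixed group would be reported as the answer to aim c. A reader could not tell whether NT-proBNP flags patients who will later be found in AF or only marks those in AF on the day. Those are different uses of the marker.

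**Working it through.** The plan states no figure for this point, so the check is mainly a reading of the text, followed by event arithmetic.

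**1. Does entry AF reach the outcome of SAP 4, item 2?**
- PPG is done at every visit (item g.e), and the entry reading counts (item g.s).
- A positive PPG leads to a 12 lead ECG (item g.j).
- Without earlier documentation the patient is not known AF (item g.l).
- Item g.m is then met at entry. Item g.p, which continues PPG at later visits in newly detected patients, fits this.
- SAP 3.1 places this patient with the cases, because the comparator must be in sinus rhythm throughout.

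So it does, on the written text.

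**2. Is there a limit elsewhere?** SAP 2.1 names a sinus-rhythm-at-baseline group, and aim a speaks of follow-up visits. Neither item g.m nor SAP 4 uses either one to define who is at risk.

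**3. AF seen only on the entry ECG (entry PPG negative).** It fails item g.m, which needs PPG detection. It is not known AF under item g.l, and it is not sinus rhythm. It has no group.

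**4. Expected cases.** Inputs: 1250 patients (Design), about 20% known AF and 4-5% newly detected AF (hypothesis a). The base for the 4-5% is ambiguous, so both are shown.
- Known AF: 0.20 × 1250 = 250, leaving 1000.
- Base 1000: 0.04 × 1000 = 40 to 0.05 × 1000 = 50 cases.
- Base 1250: 0.04 × 1250 = 50 to 0.05 × 1250 = 62.5 cases.

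**5. Later cases = cases × (1 − entry share).** The entry share is not in the documents; 25-75% is assumed.

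| Base | All cases | Later cases, 75% at entry | Later cases, 25% at entry |
|---|---|---|---|
| 1000 | 40-50 | 10-12.5 | 30-37.5 |
| 1250 | 50-62.5 | 12.5-15.6 | 37.5-46.9 |

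The overall range is about 10 to 47. Excluding patients with fewer than three measurements (Methods f) can only lower these counts.

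**6. How mixing acts on discrimination.** With a common group of non-cases and entry share f, pooled AUC = f × AUC(entry AF) + (1 − f) × AUC(later AF). As an illustration only, assume no value for later AF (AUC 0.50) and normally distributed log NT-proBNP shifted by d SD in entry AF, so that AUC(entry AF) = Φ(d/√2).
- d = 0.5: pooled AUC is 0.54 at f = 0.25 and 0.60 at f = 0.75.
- d = 1: pooled AUC is 0.57 at f = 0.25 and 0.70 at f = 0.75.

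The assumed shifts and shares alone produce these values. They show the mechanism and do not estimate its size in this study.

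**The case against.** The strongest defence reads the SAP in sequence. SAP 2.1 has only two baseline groups, sinus rhythm and known AF. SAP 3.1 then brings in follow-up data, so newly detected AF could mean leaving the sinus-rhythm group after entry. Aim a's reference to follow-up visits points the same way, and Figure 1, part of the Procedure, is not shown and might contain a timing step. This has weight: the point is an at-risk set left unstated, and the authors may have intended the narrower one. It does not close the gap. SAP 2.1 serves a different comparison, aim a's phrase belongs to aim a, and the written definition and SAP 4 carry no such limit.

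A second objection is that AF first seen after entry may be older, undetected paroxysmal AF, so restriction does not isolate onset. That is correct and belongs in the limitations. Removing AF shown to be present at entry still brings the analysis closer to aim c.

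A third is the loss of events. That is also correct, and is a reason to keep the pooled model as secondary.

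A reader might go further and infer that the newly detected rate for aim a is also wrong. The documents do not support this. The primary goal in the Background, hypothesis a's reference to the screened population, and item g.s all fit a yield that includes the entry reading.

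**Conclusion.** The point holds for aim c, hypothesis c and SAP 4, item 2. As written, the outcome for NT-proBNP includes previously undocumented AF confirmed at entry, while the question concerns AF that develops. AF seen only on the entry ECG is left without a group.

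A reader might infer that the plan will overstate NT-proBNP. That cannot be concluded: pooling raises the apparent AUC only if the marker separates entry AF better than later AF, and the documents give no values for either. What can be said is that the pooled result cannot by itself answer aim c.

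The event range (about 10 to 47 later cases, against 40 to 62 pooled) rests on the assumed 25-75% entry share and the two possible bases. The conclusion also depends on Figure 1 containing no timing rule; if it does, the written definition and the SAP should state it. One aim is affected and the correction is cheap, so it should be made.

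**What to change.** For aim c and SAP 4, item 2:

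1. **At-risk set for the main analysis:** patients without known AF and without ECG-confirmed AF at entry, whether on the entry ECG or on the ECG that follows a positive entry PPG. This is in line with the sinus-rhythm group of SAP 2.1.
2. **Outcome:** AF first confirmed on a 12 lead ECG after a positive PPG at a reading later than entry.
3. **Unconfirmed positive entry PPG:** these patients stay at risk and can become cases. A sensitivity analysis excludes them.
4. **Entry AF:** report its association with NT-proBNP separately, as diagnostic. Assign AF seen only on the entry ECG to this group.
5. **Pooled model:** keep it as secondary.
6. **Limitation:** state that first confirmation after entry is not proof of onset after entry.

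**Cost.** Only the wording of item g.m and the SAP changes, because the entry ECG, entry PPG and later readings are already planned. The price is fewer events and wider intervals. At 10 events per parameter (a rule of thumb, assumed here), rounding down, 10 to 37.5 later cases support 1 to 3 parameters (base 1000) and 12.5 to 46.9 support 1 to 4 (base 1250). The pooled outcome supports 4 to 5 or 5 to 6. Hypothesis c already combines NT-proBNP with geriatric assessment findings and CHA₂DS₂-VASc, so predictors must be few and named in advance.
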